8.2.9. Days of Hospitalization

Duration of hospitalization days will be summarized in a table using medians and quartiles by treatment arm (Table 47). Incidence of readmittance will also be summarized. Analyses will be performed in the ITT population, Treated population, and a subset of the Treated population of treated subjects only as subjects who are not treated are terminated from the study immediately and are included in the ITT/Treated analyses with a count of 1 day. Bee swarm plots of days hospitalized by treatment arm will be generated, where subject whose days are imputed to the maximum of 28 days due to death are grouped separately from subjects who do not die.

8.3. Exploratory Efficacy Analyses

Analyses of exploratory outcome measures are not covered in this SAP.

9. SAFETY EVALUATION

9.1. Demographic and Other Baseline Characteristics

Summaries of age, sex, height, weight, BMI, ethnicity, and race will be presented by treatment group as well as geographic region, duration of symptoms prior to enrollment, and disease severity (Table 49 and Table 50). Ethnicity will be categorized as Hispanic or Latino, or not Hispanic and not Latino. In accordance with NIH reporting policy, subjects may self-designate as belonging to more than one race or may refuse to identify a race, the latter reflected in the CRF as “No” to each racial option. Both demographic tables will be repeated to assess baseline differences between remdesivir subjects, placebo subjects who are not retreated with remdesivir, and placebo subjects who are retreated with remdesivir (Table 51 and Table 52).

Individual subject listings will be presented for all demographics and baseline characteristics (Listing 7).

9.1.1. Prior and Concurrent Medical Conditions

Focused medical history is obtained at the screening visit that includes the following:

- Day of onset of COVID-19 symptoms
- History of chronic medical conditions related to inclusion and exclusion criteria
- Medication allergies
- Review medications and therapies for this current illness.

Medical history is limited to the following conditions: asthma, cancer, chronic kidney disease, chronic liver disease, chronic oxygen requirement, chronic respiratory disease, congestive heart failure, coronary artery disease, diabetes I and II, hypertension, immune deficiency, and obesity. All current illnesses and past pre-existing medical conditions will be MedDRA® coded using MedDRA dictionary version 22.0 or higher. Summaries of subjects’ pre-existing medical conditions will be presented by treatment group (Table 53).

Individual subject listings will be presented for all medical conditions (Listing 8).

9.1.2. Prior and Concomitant Medications

Medication history (concomitant medications) includes a review of all current medications and medications taken within 7 days prior to enrollment through approximately Day 11 or early termination (if Day 11), whichever occurs first.

Summaries of medications that were started prior to dosing and continuing at the time of dosing will be presented by WHO Drug Terms 2 and 3 and treatment group (Table 54). Summaries of overall use of prohibited medications/therapies listed in Section 6.4 as well as use by select study days will also be generated (Table 55 and Table 56).

Individual subject listings will be presented for all concomitant medications (Listing 9).

9.2. Measurements of Treatment Compliance

The subject disposition table will summarize the number of subjects that were screened, randomized, received a loading dose, received all maintenance doses, each maintenance dose, completed all blood draws, and completed Study Day 29 visit. In addition, the number of subjects with halted, slowed, or missed doses will be summarized by treatment arm (See Section 7).

Individual subject listings will be presented for all subjects who discontinued dosing (Listing 2).

Individual subject listings will be presented for all subjects who missed, halted or slowed any doses (Listing 10).

9.3. Adverse Events

For the calculation of incidence of adverse events (i.e., on a per subject basis), each subject will only be counted once and any repetitions of adverse events within a subject will be ignored; the denominator will be the number of subjects in the Treated population. All adverse events reported will be included in the summaries and analyses.

An overall summary by treatment arm and disease severity of adverse events is presented that includes subjects with at least one event, at least one related event, at least one SAE, at least one related SAE and at least one AE leading to early termination (Table 57).

Adverse events occurring in 5% of subjects (by MedDRA preferred term) in any treatment group will be presented (Table 58).

The proportion of subjects reporting at least one adverse event will be summarized by MedDRA system organ class and preferred term for each treatment arm, disease severity and overall. Denominators for percentages are the number of subjects in the Treated population.

The following summaries for adverse events will be presented by MedDRA system organ class, preferred term, disease severity and treatment group:

- Subject listing of non-serious adverse events (Listing 11);
- Bar chart of non-serious related adverse events by severity and MedDRA system organ class (Figure 21);
- Bar chart of non-serious related adverse events by maximum severity and MedDRA system organ class (Figure 22);

All the summaries described in this section will be generated for both the early and the full analysis sets.

9.4. Deaths, Serious Adverse Events and other Significant Adverse Events

A listing of death and other serious adverse events will be presented, including Subject ID, treatment group, Adverse Event Description, Associated Dose Number, Number of Days Post Dose (Duration), Number of Days Post Dose the Event Became Serious, Reason Reported as an SAE, Severity, Relationship to Treatment, Alternate Etiology if not Related, Action Taken with

Study Treatment, Subject Discontinuation, Outcome, MedDRA SOC, and MedDRA PT (Listing 12 and Listing 13).

The number of subjects who die by Day 15 and Day 29 will be presented by treatment arm. The 14- and 28-day crude mortality rate, which will use the number of subjects in the treatment group and analysis population as the denominator, will be presented (Table 59). The analysis will be repeated censoring placebo subjects who were retreated with remdesivir at the time of retreatment.

Mortality through Day 15 and 29 will also be analyzed as a time to event endpoint (see Section 3.3). A table will present median time to event along with 95% confidence intervals overall for each treatment arm along with the hazard ratio estimate and log rank p-values (Table 61). Differences in time-to-event endpoints by treatment will be summarized with Kaplan-Meier curves (Figure 23). Analyses of mortality will be performed in the ITT and the Treated analysis populations and will be performed on both the early and the full analysis sets.

The ITT tabular summaries will be repeated censoring placebo subjects who were retreated with remdesivir at the time of retreatment. Similarly, the summaries will be repeated censoring subjects who were unblinded at the time of unblinding.

Rates of Grade 3 and 4 AE occurrence will be compared between treatment arms using Barnard's exact test and presented (Table 63). Rates of SAE occurrence will also be compared between treatment arms using Barnard's exact test and presented. Further, the composite endpoint of the occurrence of death, SAE, or Grade 3 or 4 AE described in Section 3.3 will be analyzed as a time to event outcome. A table will present median time to event along with 95% confidence intervals overall for each treatment arm along with the hazard ratio estimate and log rank p-values (Table 64). Differences in time-to-event endpoints by treatment will be summarized with Kaplan-Meier curves (Figure 24).

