3.3.10. Time to Death

For analysis of time to death, the time to death will be defined as the elapsed time (in days) from randomization (or treatment administration for the safety analysis) to death. Any subjects that are lost to follow-up or terminated early prior to death will be censored at the day of their last observed assessment or last captured event (e.g. the end date of an adverse event). If it is learned that a subject who terminated early had subsequently died prior to Day 29, then the subject will be classified as dead. Subjects who complete follow-up will be censored at the earliest of their Day 29 visit and (actual Day 29). Deaths that occur after Day 29 will be censored at Day 29.

Similar censoring methods will be used for the 14-day mortality analyses in that deaths that occur after Day 15 will be censored at Day 15 and subjects who are confirmed alive through Day 15 will be censored at Day 15. Subjects whose last observed assessment or last capture event (e.g. the end date of an adverse event) is prior to Day 15 will be censored at that last observed assessment/event.

Sensitivity analyses will be performed where subjects who were unblinded and retreated with remdesivir will be censored at the time of remdesivir treatment initiation. A similar process will be used for the unblinding sensitivity analysis.

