4. INVESTIGATIONAL PLAN

4.1. Overall Study Design and Plan

This study is an adaptive, randomized, double-blind, placebo-controlled trial to evaluate the safety and efficacy of novel therapeutic agents in hospitalized adults diagnosed with COVID-19. The study is a multicenter trial that will be conducted in up to approximately 100 sites globally. The study will compare different investigational therapeutic agents to a control arm. There will be interim monitoring to allow early stopping for futility, efficacy, or safety. If one therapy proves to be efficacious, then this treatment may become the control arm for comparison(s) with new experimental treatment(s). Any such change would be accompanied by an updated sample size. Because background standards of supportive care may evolve/improve over time as more is learned about successful management of COVID-19, comparisons of safety and efficacy will be based on data from concurrently randomized subjects. An independent Data and Safety Monitoring Board (DSMB) will actively monitor interim data to make recommendations about early study closure or changes to study arms.

Recruitment will continue until there are 400 subjects with a “recovered” status (per the primary objective). The primary analysis will be based the total number of subjects enrolled to achieve 400 recoveries. An additional analysis of the moderate severity subgroup (those with baseline status of “Hospitalized, requiring supplemental oxygen” or “Hospitalized, not requiring supplemental oxygen - requiring ongoing medical care”) is also of public health importance. Hence, enrollment will be permitted until the date of April 20, 2020 to ensure 400 recoveries and provide additional data about this important subgroup. With recent enrollment rates, the total sample size may be 600 to over 800.

If any additional therapeutic arms are added, the sample size will be recalculated.

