6.2.3. Final Analyses

After the DSMB meeting on April 27, 2020, the interim results were provided to the sponsor and the interim analyses were performed again on an April 28, 2020 database freeze (unlocked dataset). The results of these analyses were made public on April 29, 2020. Subsequent to this, the plan for the final analyses (and corresponding datasets) was modified to the following:

- A preliminary analysis of the primary, key secondary, and major safety outcomes will be performed on unlocked, partially clean version of data and events that occurred up to April 28, 2020. This preliminary analysis dataset was used for the analyses and summaries included in the “Remdesivir for the Treatment of Covid-19 – Preliminary Report” article published in The New England Journal of Medicine on May 22, 2020 (DOI: 10.1056/NEJMoa2007764) and will be used for the preliminary report, whose summaries will coincide with the summaries provided in the article. This dataset will not be used for any further analyses apart from the preliminary report.
- A fully cleaned and locked version of data and events that occurred up to April 28, 2020 will be denoted as the “early analysis set”. Section 7, Section 8, and Section 9 denote which summaries will be provided as part of this report, but will focus largely on primary outcome, key secondary outcome, and mortality.

- The final analyses of all outcomes and planned summaries/listings will be performed on the final full locked database and provided in an addendum to the final report. This is the fully cleaned and locked version of all data and events that occurred at any time during this trial and will be denoted as the “full analysis dataset”.

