At least one serious adverse event	X	x	x	x	x	x	x	x	x	x	x	x	x	x	x	x	x	x
At least one related serious adverse event	X	x	x	x	x	x	x	x	x	x	x	x	x	x	x	x	x	x
At least one adverse event leading to early termination ^b	X	x	x	x	x	x	x	x	x	x	x	x	x	x	x	x	x	x
At least one Unanticipated Problem	X	x	x	x	x	x	x	x	x	x	x	x	x	x	x	x	x	x
N = Number of subjects in the Treated Population																		
^a Subjects are counted once for each category regardless of the number of events.																		
^b As reported on the Adverse Event eCRF.																		
All Grade 3 and 4 AEs are captured as AEs. In addition, any Grade 2 or higher suspected drug-related hypersensitivity reaction is reported as an AE.																		

Table 58: Adverse Events Occurring in 5% of Subjects in Any Treatment Group by MedDRA System Organ Class and Preferred Term, and Treatment Group - Treated Population

Preferred Term	MedDRA System Organ Class	Remdesivir (N=X)			Placebo (N=X)			All Subjects (N=X)		
		n	%	Events	n	%	Events	n	%	Events
Serious Adverse Events										
PT1	SOC1	x	x	x	x	x	x	x	x	x
Etc.	Etc.	x	x	x	x	x	x	x	x	x
Other (Non-serious) Adverse Events										
PT1	SOC1	x	x	x	x	x	x	x	x	x
Etc	Etc	x	x	x	x	x	x	x	x	x
N = number of subjects in the Treated Population (number of subjects at risk). n = number of subjects reporting event. Events = total frequency of events reported.										

Programming Notes:

Select all preferred terms/System organ classes where the % for any treatment group or overall is $\geq 5\%$.
Sort preferred terms by descending order of frequency.

Table 59: Deaths by Day 15 or Day 29 by Treatment Group

Analysis Population	Study Day	Remdesivir (N=X)			Placebo (N=X)		
		n	Mortality Rate	Rate 95% CI	n	Mortality Rate	Rate 95% CI
ITT Population	Day 15	x	x.x	x.x, x.x	x	x.x	x.x, x.x
	Day 29	x	x.x	x.x, x.x	x	x.x	x.x, x.x
Treated Population	Day 15	x	x.x	x.x, x.x	x	x.x	x.x, x.x
	Day 29	x	x.x	x.x, x.x	x	x.x	x.x, x.x

N = Number of Subject in the specified treatment group and analysis population.
n = Number of subjects in a given treatment group who died by the given timepoint

Table with similar format:

Table 60: Deaths by Day 15 or Day 29 by Treatment Group – Unblinding and Crossover Treatment Sensitivity Analysis

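### In the early analysis set, the crude 14- and 28-day mortality rates count subjects who could not yet have reached Day 15 or Day 29, so absolute mortality is understated in both arms

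*SAP*

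**What the plan says.** Three parts of the SAP combine here.

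- **The data cut.** Section 6.2.3 defines the early analysis set: "A fully cleaned and locked version of data and events that occurred up to April 28, 2020 will be denoted as the" early analysis set. It sets no minimum follow-up, and says the report on this set "will focus largely on primary outcome, key secondary outcome, and mortality". Section 4.1 states that "enrollment will be permitted until the date of April 20, 2020".
- **The estimator.** Section 9.4 presents crude 14- and 28-day mortality, "which will use the number of subjects in the treatment group and analysis population as the denominator, will be presented". In the Table 59 shell, N is everyone in the arm and population, and "n = Number of subjects in a given treatment group who died by the given timepoint". Section 6.3.1 defines ITT and Treated without any follow-up requirement. Section 15 records the all-subject denominator as a deliberate clarification.
- **The scope.** Section 9.4 says the mortality analyses "will be performed on both the early and the full analysis sets". Nothing exempts Table 59.

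Section 9.4 also plans a time-to-death analysis with Kaplan-Meier curves. Its Table 61 shell shows the median, hazard ratio and p-value, but no Kaplan-Meier mortality at Day 15 or Day 29. For the 14-day analysis, Section 3.3.10 says that a subject whose last assessment or captured event "is prior to Day 15 will be censored at that last observed assessment/event". Its Day 29 wording covers subjects lost, terminated early or completing follow-up. It does not say what happens to a subject still on study at April 28.

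**The concern.** A crude rate at a fixed horizon is a valid estimate of mortality only if everyone in the denominator has been followed to that horizon or has died. In the early set, late-randomized subjects are in the denominator, but their deaths after April 28 and before the horizon cannot enter the numerator. The error therefore runs one way, downward, in both arms.

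Mortality is one of three outcomes the early report is built around. The figure labelled 28-day mortality would mix full and partial follow-up, and would sit below the later full-set figure partly because of the cut date alone. Table 59 has no difference column, but readers will subtract the two rates. That difference is also understated if it grows with follow-up. If the curves converge, the error can go the other way.

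**Working it through.** The plan gives no mortality figure for the early set, so there is nothing of its own to reproduce.

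**Inputs from the documents.** Cut April 28, 2020 (SAP 6.2.3). Last enrollment April 20 (SAP 4.1). Highest control-arm death proportion at Day 15 in the planning scenarios, 3% (SAP Table 4). Accrual had begun by March 2: the protocol's version 2.0 amendment entry of that date mentions the first enrollment. The version 3.0 entry mentions a rapid pace of enrollment but gives no figures.

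**Assumed, because the documents are silent.** Accrual start between February 1 and March 2. Accrual either even or doubling every 20 days. True 28-day mortality 10%. Death times either even over 28 days or front-loaded (exponential weights, mean 10 days).

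**Step 1: who is short of follow-up.** Follow-up = April 28 minus randomization date. April 1–20 (20 days of accrual) is short of 28 days; April 15–20 (6 days) is short of 14 days.
- Even accrual, February 1 start (80 days): 20/80 = 25.0% and 6/80 = 7.5%.
- Even accrual, March 2 start (50 days): 20/50 = 40.0% and 6/50 = 12.0%.
- Doubling every 20 days: 53.3% (February 1) and 60.7% (March 2) short of 28 days.

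**Step 2: share of deaths captured.** Expected crude rate ÷ true rate = Σ w(day) × F(min(follow-up, H)) / F(H), where w is the accrual weight, F the cumulative death-time distribution and H is 14 or 28.

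With even accrual and even deaths, the last 20 accrual days have 8 to 27 days of follow-up. These sum to 350, and 350/28 = 12.5 full-follow-up equivalents. February 1 start: (60 + 12.5)/80 = 90.6%. March 2 start: (30 + 12.5)/50 = 85.0%.

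| Accrual | Start | 28-day deaths captured, even / front-loaded | True 10% reads |
|---|---|---|---|
| Even | Feb 1 | 90.6% / 96.2% | 9.1% / 9.6% |
| Even | Mar 2 | 85.0% / 93.9% | 8.5% / 9.4% |
| Doubling | Feb 1 | 77.8% / 90.6% | 7.8% / 9.1% |
| Doubling | Mar 2 | 74.7% / 89.3% | 7.5% / 8.9% |

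At 14 days the capture is 97.0% to 98.9% with even accrual and 94.1% to 97.0% with doubling. A true 3% then reads 2.91% to 2.97%, or 2.82% to 2.91%.

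A separate calculation with steeper accrual (up to 7-day doubling) and other death timings widens the 28-day range: 10% reads 5.8% to 9.7%. The relative 14-day shortfall reaches 12% at the extreme.

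**Step 3: arm difference, even accrual.** True 12% vs 8% with even deaths: 12 × 0.906 − 8 × 0.906 = 3.6 points (February 1) and 12 × 0.85 − 8 × 0.85 = 3.4 points (March 2), instead of 4.0. If both arms reach 10% but one arm's deaths come early (mean 5 days), a true difference of 0 reads 9.87 − 9.06 = 0.8 or 9.80 − 8.50 = 1.3 points.

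**Step 4: does Kaplan-Meier repair it?** Simulation with 350 per arm, true 10%, and even accrual and deaths. It assumes that 80% of survivors are discharged on Days 4–20 and that 15% of deaths follow discharge.

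| Estimator | Feb 1 start | Mar 2 start |
|---|---|---|
| Crude | 9.0 | 8.4–8.5 |
| Kaplan-Meier, censored at last contact | 10.1 | 10.3–10.4 |
| Kaplan-Meier, censored at April 28 | 9.9–10.0 | 9.9–10.0 |

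With 20-day doubling, last-contact censoring reads 10.2–10.6 and April 28 censoring 9.8–10.0.

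**The case against.** The strongest defence is that the rate is openly called crude, its denominator is stated, and the same section plans a censored analysis on both sets. The full analysis set later removes the problem. On this view only one descriptive table in one data cut is affected, and its size rests on assumptions. SAP Section 17 also allows extra data points in any table.

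Much of this is fair, but it does not remove the point. The hazard ratio, the log-rank test and the full set are indeed unaffected, and the relative comparison is nearly preserved if death timing is similar in the arms. The converging-curves case is a constructed example. But Section 17 permits additions without committing to any, and no planned table gives follow-up-corrected absolute mortality. The full-set results come in an addendum, after the early report.

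Four narrower objections stand as refinements:
- The count of observed deaths is a legitimate description and can stay.
- April 28 censoring came closer to the truth in the simulation than last-contact censoring, so it is arguable which should lead.
- Table 34 has separate rows for missing scores, so incomplete data would be partly visible there.
- Section 9.4 plans mortality analyses in ITT and Treated, but the listed Figure 23 is titled for the Treated population only, which makes the curves a weaker safeguard.

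**Conclusion.** The concern holds. Followed as written, the SAP understates absolute early-set mortality in both arms. The direction follows from the dates and the denominator alone. The size cannot be determined from the documents, because they give neither the accrual curve nor a 28-day mortality assumption nor the timing of deaths.

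Under the main assumed scenarios, a true 28-day mortality of 10% reads 7.5% to 9.6%, and lower still if accrual was steeper. At 14 days the effect is small against the SAP's 1% to 3% planning figures: at most about 0.2 points at 3%. It should be fixed, but it does not touch the primary analysis or the formal mortality comparison.

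**What to change.** 1. **Section 9.4 and Table 59 (or Table 61), early set, ITT and Treated.** In place of the crude rate, give Kaplan-Meier mortality at Day 15 and Day 29 by arm with 95% CI, the arm difference with 95% CI, and the number with at least 14 and 28 days of potential follow-up at April 28, 2020. Observed death counts can remain. Keep the crude rate for the full set.
2. **Section 3.3.10.** Extend the 14-day rule, for example: *For the early analysis set, subjects not known to have died by April 28, 2020 will be censored at their last observed assessment or captured event on or before that date, and no later than actual Day 29 (actual Day 15 for the 14-day analysis).*
3. **Sensitivity analysis.** Repeat with censoring at the earlier of April 28 and actual Day 29. Discharged subjects are seen only at Days 15, 22 and 29, so last-contact censoring can read slightly high and April 28 censoring slightly low. Either may lead if both are shown.
4. **Tables 22 and 34.** Both use the all-ITT denominator, and the SAP does not clearly assign them to the early set. If they are produced for it, footnote the incomplete follow-up.
5. **Figure 23.** Align its listed population with Section 9.4.

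The cost is a few sentences, some table cells and one sensitivity row, with no new data. Intervals widen. With an assumed 350 per arm and 10% mortality, the per-arm standard error at Day 29 rises from about 1.5–1.6 points (crude) to 1.7–1.9 under even accrual, and to about 1.9–2.1 with 20-day doubling and even death timing.

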3.3.2. Recovery and Time to Recovery

The primary efficacy outcome measure is the time to recovery. Recovery will be defined as having a value of 1, 2, or 3 on the clinical status 8-point ordinal scale. The time to recovery will be defined as the elapsed time (in days) from randomization to the earliest day at which a subject reaches recovery. Note that since clinical status assessments are recorded as defined in Section 4.3, the day that is being assessed (not necessarily the day the response is collected) will be used to determine the timing of events. For example, a subject with a score of 5 recorded on Days 1 - 3 and a score of 3 recorded on Day 4 will have a time to recovery equal to 3 days. It is also possible that a subject has a clinical status score > 3 reported for a particular day but was subsequently discharged on the same day. For these scenarios where a subject is discharged with no reported clinical score of 1, 2, or 3 will be considered recovered at the time of discharge.

Any subjects that are lost to follow-up or terminated early prior to an observed recovery will be censored at the day of their last observed assessment. Subjects who complete follow-up but do not experience recovery will be censored at the day of their Day 29 visit. All deaths within Day 29 (and prior to recovery) will be considered censored at 28 days. Note that we do not expect many subjects to worsen after discharge.

However, we will evaluate whether any discharged subjects subsequently experience a worse clinical status and sensitivity analyses will be conducted accordingly. For these analyses, subjects who recover but are later re-admitted will not be considered a recovery but will instead be censored at 28 days. Sensitivity analyses will be performed where subjects who were crossover treated with remdesivir (per April 29, 2020 Protocol Administrative Letter) will be censored at the time of remdesivir treatment initiation. In addition, the analyses will be replicated where subjects who were unblinded, regardless of whether they received crossover treatment of remdesivir or not, will be censored at the time of unblinding.

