4.2.6. Blinding

The treatment will be prepared by the licensed pharmacist and administered by blinded study personnel or hospital staff. All follow-up safety and efficacy evaluations will be performed by blinded clinic staff.

The unblinded pharmacist at each site will refer to the Treatment Key provided for the trial by the SDCC to determine the treatment for the subjects. The pharmacist will maintain an open label code (provided by the SDCC) under locked/secured conditions and will follow the randomization code. Due to limitation on placebo supplies, normal saline may be given at an equal volume as a placebo in place of the lyophilized formulation. In this case, IV bags of study treatment (both Remdesivir and placebo) will be covered to mask the slight color difference between the Remdesivir solution and placebo to maintain the study blind.

After the public disclosure of the interim results, an unblinding procedure was added (per April 29, 2020 Protocol Administrative Letter) in which an investigator could unblind a subject and potentially initiate remdesivir treatment if one of the following criteria is met:

1. Potential remdesivir treatment, only for subjects meeting all of the following criteria:
 - a. On study (i.e. have not completed the Day 29 visit)
 - b. Hospitalized
 - c. It is clinically indicated (i.e., those that are doing poorly)
2. Subject/LAR request, only for subjects meeting one of the following criteria:
 - a. Subject is no longer hospitalized and has completed the study (on or after Day 29 visit), or
 - b. After death.

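### In the full analysis set, the crossover version of crude mortality (Table 60) counts crossed-over placebo subjects as non-deaths, and the censored time-to-event versions are informatively censored

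*SAP*

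**What the plan says.** **Who can cross over.** SAP 4.2.6 describes a procedure added by an April 29, 2020 letter, after the interim results were public: "an investigator could unblind a subject and potentially initiate remdesivir treatment if one of the following criteria is met". For treatment during the study, the subject must not have completed the Day 29 visit, must be hospitalized, and must meet a third condition: "It is clinically indicated (i.e., those that are doing poorly".

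**Crude mortality.** SAP 9.4 plans a 14- and 28-day "crude mortality rate, which will use the number of subjects in the treatment group and analysis population as the denominator" (Table 59). It then says: "The analysis will be repeated censoring placebo subjects who were retreated with remdesivir at the time of retreatment". No new denominator is given. Table 60 takes the Table 59 format, whose footnote reads "N = Number of Subject in the specified treatment group and analysis population". The programming note for Table 60 replaces one column and leaves N alone.

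**Time to death.** SAP 3.3.10: "Sensitivity analyses will be performed where subjects who were unblinded and retreated with remdesivir will be censored at the time of remdesivir treatment initiation". SAP 9.4: "The ITT tabular summaries will be repeated censoring placebo subjects who were retreated with remdesivir at the time of retreatment" (Table 62, in the Table 61 format of median time, hazard ratio and p-value).

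**Time to recovery.** Under SAP 3.3.2, crossed-over subjects "will be censored at the time of remdesivir treatment initiation" (Table 20).

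The SAP also describes the crossovers: status around retreatment (Table 21), individual courses (Figure 9) and baseline characteristics (Tables 51 and 52). I found no weighting, adjustment or bound for the censoring in the mortality or recovery sections.

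**The concern.** There are two separate defects.

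The first is in the estimator. Censoring has a meaning only where there is a risk set. Applied to a proportion with a fixed denominator, it deletes the crossover's later death from the numerator and keeps the subject below the line. The result equals the ITT rate minus post-crossover placebo deaths divided by N, so it can never exceed the ITT rate. Yet if crossover treatment had prevented deaths, placebo mortality without crossover would be higher than ITT. Table 60 cannot move in the direction it would need to show.

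The second is selection. Crossover is open only to subjects with a poor current course, so censoring at crossover depends on prognosis. The subjects left at risk, who include those already discharged, stand in for subjects likely to do worse.

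At stake is how these rows are read. A treatment difference that shrinks in them may look like fragility of the ITT result when, for the crude rate, the direction of the placebo shift was fixed by construction.

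**Working it through.** The documents give no Day 29 mortality assumption, no crossover count and no expected bias, so there is no stated figure to reproduce. Every rate below is an assumption. N = 300 to 400 per arm follows from the planned total of 600 to over 800 at 1:1.

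**Formulas, one crossover time c.** N placebo subjects; d1 deaths before c; K crossovers at c; d2 later deaths among the others; q = a crossover's risk of death from c to Day 29 had they not crossed over.

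- No-crossover risk = (d1 + d2 + Kq)/N
- Crude, censored, full denominator = (d1 + d2)/N; error = −Kq/N
- Kaplan-Meier, censored = 1 − (1 − d1/N)(1 − d2/(N − d1 − K))
- All crossovers die = (d1 + d2 + K)/N

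The crude error is never positive, and it is strictly negative once Kq > 0, whatever the reason for crossing over. The censored crude figure is in fact the lower bound in which every crossover survives.

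**One case in full.** N = 400, 7% dead before c, 3% later risk in the others, K = 20, q = 0.50. Then d1 = 28, d2 = 0.03 × 352 = 10.56, Kq = 10.

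- No crossover: 48.56/400 = 12.1%
- Crude, censored: 38.56/400 = 9.6%
- Kaplan-Meier: 1 − 0.93 × 0.97 = 9.8%
- All crossovers die: 58.56/400 = 14.6%
- Crossovers dropped from the denominator: 38.56/380 = 10.1%
- ITT, if crossover halved their risk: (38.56 + 5)/400 = 10.9%

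In this case both censored figures lie further from 12.1% than the ITT rate does.

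**Other assumed values (N = 400, same 7% and 3%).**

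| K | q | No crossover | Crude | KM | All die |
|---|---|---|---|---|---|
| 10 | 0.25 | 10.3% | 9.7% | 9.8% | 12.2% |
| 20 | 0.25 | 10.9% | 9.6% | 9.8% | 14.6% |
| 40 | 0.50 | 14.5% | 9.5% | 9.8% | 19.5% |

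Over N = 300 to 400, K = 5 to 40 and q = 0.10 to 0.50, crude is low by 0.13 to 6.7 points and Kaplan-Meier by 0.09 to 6.3. With q = 0.02, below the others' 3%, Kaplan-Meier is slightly high (0.01 to 0.13 points) and crude is still low.

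**Separating the two defects.** A simulation used 400 per arm, true hazard ratio 1, a quarter of subjects with 40% 28-day mortality and the rest 2%, and crossover between Days 10 and 28.

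- Crossover unrelated to prognosis: Kaplan-Meier matched the truth (11.4%, 11.5%, 11.3%), while crude fell to 11.1%, 10.7% and 9.7%.
- Crossover only in poor-prognosis subjects (about 7, 18 and 35 of them): true 11.5% to 11.6%; crude 11.2%, 10.8%, 10.4%; Kaplan-Meier 11.2%, 11.0%, 10.6%; mean hazard ratio (remdesivir/placebo) 1.02, 1.04, 1.10.

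The prognosis-free runs, where the ratio should be 1, gave 1.00 to 1.02. Only the largest ratio stands well clear of simulation noise.

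**Recovery.** Another simulation let 4.5% to 9% of placebo subjects cross over, with no effect of crossing over. The recovery ratio of 1.233 became 1.226 to 1.219 with censoring (error 0.007 to 0.014), and 1.257 to 1.282 with crossovers kept at risk as not recovered (error 0.024 to 0.049). The death hazard ratio of 0.55 became 0.57 to 0.60 with censoring.

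**Scope by date.** The early analysis set stops at April 28, before the letter. With enrollment closing on April 20 as planned, the last enrollee is at Day 10 on April 29. An April 16 enrollee is at Day 14 and an April 15 enrollee at Day 15. The Day 15 row can therefore be touched only by April 16–20 enrollees.

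**The case against.** **The denominator is inferred.** SAP 9.4 does not restate it for the repeated analysis, and SAP 6.3.1 speaks of crossovers being either censored or excluded. This has some force. But 6.3.1 points to Sections 3 and 8, not 9.4, and retention is the plain reading of 9.4 and the Table 59 shell. Exclusion is right only if the crossovers' risk equals the rate in everyone else; it gives 10.1% against 12.1% above.

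**Kaplan-Meier barely helps.** This stands. In the worked case it recovers under 0.2 of 2.5 points. It cures the arithmetic and not the selection, so it needs a bound beside it.

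**The not-recovered row is worse than the censored one.** This also stands: its error is about three and a half times as large, and it favours remdesivir. It is useful only as a labelled limit.

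**The SAP already gives context.** The descriptive tables and Figure 9 show who was censored, p-values are withheld for sensitivity analyses of the primary outcome, and SAP 15 says only that these analyses explore the crossovers. All true, but none of it corrects the Table 60 figure.

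Stronger readings that a reader might infer, and that the documents do not support:

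- *All placebo subjects doing poorly are censored.* SAP 4.2.6 leaves crossover to the investigator, so some remain.
- *Every censored analysis must understate placebo mortality.* That is arithmetic for the crude rate only.
- *The ITT or primary result is compromised, or a benefit is manufactured.* The uncensored ITT analyses are kept, and the expected direction works against remdesivir.
- *The unblinding analysis is biased the same way.* It can censor subjects in both arms, so this one-sided direction does not carry over.

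**Conclusion.** The point holds within these limits. As written, the crossover version of crude placebo mortality in Table 60 is too low by Kq/N whenever any crossover would have died, and it cannot exceed the ITT rate. This rests on reading the denominator as the whole arm, which is what SAP 9.4 and the table shell say.

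The censored time-to-death and time-to-recovery analyses are informatively censored under the rule in SAP 4.2.6. Their expected bias is toward no treatment effect, but that is not certain: it requires crossovers to have a worse outlook than the subjects left at risk.

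The size cannot be determined from the documents. Under the assumed values the mortality error runs from about 0.1 to over 6 percentage points, and the recovery ratio shifts only in the second decimal. Only crossover sensitivity results in the full analysis set are affected.

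**What to change.** - **Table 60, crossover rows.** Replace the censored crude proportion with the Kaplan-Meier Day 15 and Day 29 mortality estimate and its confidence interval. No planned table gives this; Table 62 shows medians and hazard ratios. Set beside it the uncensored ITT rate and a bound counting all crossovers as deaths.
- **Table 20.** Add a row that keeps crossovers at risk as not recovered to Day 29, the treatment SAP 3.3.2 already gives deaths. Label it as a bound that favours remdesivir. With the censored row it brackets the result, provided the censored row errs in the expected direction.
- **Labels.** Footnote every row censored at crossover as informatively censored.
- **Optional.** Inverse-probability-of-censoring weights using the latest ordinal score and severity. This needs a time-varying censoring model fitted on possibly few crossovers, so it should not be required.

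The cost is one changed estimator, a few extra rows from data already collected, and a range that looks wider.
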